8.6.1.2 Analysis of Second Efficacy Variable

Age correlation with SUV_r

Pearson's correlation coefficient will be used to determine the correlation of age with mean SUV_r from cognitively healthy individuals.

Descriptive statistics will be performed according to cognitively healthy subject category and by the age groups. Subjects are divided to the age group of: YCN 20-40, OCN 50-59, OCN 60-69, OCN 70-79, and OCN ≥ 80 .

Box plot (including individual data points plotted) for overall SUVr will be generated for all cognitively healthy subject categories by age group: YCN 20-40, OCN 50-59, OCN 60-69, OCN 70-79, and OCN ≥ 80 .

8.6.1.3 Exploratory Analyses

8.6.1.3.1 Correlations between Flortaucipir uptake and cognitive impairment

This analysis will be limited to the subjects with an amyloid beta positive (AB+) status. Partial Pearson's correlation analysis adjusted for age will be conducted.

The correlation analyses will be conducted between these measurements: baseline MUBADA SUVr versus baseline ADAS total, MMSE, and FAQ scores.

To visually explore the cognitive domain relationship with flortaucipir uptake, scatter plots will be generated between the variables as described above.

8.6.1.3.2 Correlations between Flortaucipir SUVr uptake and Biomarkers of neurodegeneration and neurological disease.

Correlations analysis will be used to evaluate the association between baseline flortaucipir MUBADA SUVr results and florbetapir SUVr, with Pearson's correlation. Correlations will be completed using all subjects except for YCN.

Scatter plot between MUBADA SUVr and florbetapir SUVr will be created to visually display the relationship, with diagnosis shape coded.

Correlations will be used to evaluate the association between flortaucipir SUVr results and the atrophy assessed by volumetric MRI (whole brain, volume, total ventricle size, total gray volume). Correlations will be completed for AD/MCI subjects.

The relationship between genetic markers including ApoE and MAPT will be assessed using ANCOVA models. The analysis will include all subjects except for YCN. For the ANCOVA model, MUBADA SUVr values will be used as dependent variable, and independent variables include ApoE E4 status (carriers vs. non-carriers), Amyloid status (AB+ vs. AB-), interaction of ApoE E4 status and amyloid status, and age. LS means of

AB+, AB-, E4 carriers, non E4 carriers, AB+ E4 carriers, AB+ non E4 carriers, AB- E4 carriers, AB- non E4 carriers will be calculated through proper contrast set up, along with the 95% CI.

Scatter plot of MUBADA SUV_r values, overlay with box plots by MAPT genotypes (H1/H1, H1/H2 and H2/H2) will be used to display the tau load level by MAPT genotypes. If there are notable differences across MAPT genotypes, further analyses will be carry out accordingly, which will not be detailed in this SAP.

8.6.1.3.3 Multi-variate models to explore possible factors for cognitive impairments

To further explore the possible factors for cognitive impairment, multivariate models will be conducted. The following variables will be used as dependent variables for each of these models: ADAS Cog 11, MMSE, and FAQ. Each of these models will include these variables as independent variables: baseline age, ANART, MUBADA SUV_r, florbetapir SUV_r, whole brain volume, and ApoE E4 status. Stepwise selection technique will be used to build the most parsimonious model, with entry and stay selection p-value set at 0.2. The analyses will be run separately with all subjects except for YCN, and with AB+ subjects only.

8.6.2 Exploratory Phase, Longitudinal Analysis

8.6.2.1 Analysis of Primary Efficacy Variable

Mixed Model Repeated Measures for Evaluation of Flortaucipir SUV_r over time

Descriptive summary statistics for Flortaucipir SUV_r will be provided by amyloid beta status (AB+, AB-) at baseline, 9 month, and 18 month across all subjects.

Change from baseline for Flortaucipir SUV_r will be estimated using repeated measures models for all subjects except for YCN subjects (who do not have follow-up flortaucipir scans at 9 months and 18 month). Due to the concern of unequal variance for flortaucipir SUV_r changes by amyloid status, the model will be run for AB+ subjects only, and for AB- subjects only separately. For this analysis, time will be considered to be categorical variable. A mixed model will be run with MUBADA SUV_r change from baseline as dependent variable, baseline MUBADA SUV_r and age, and visit as independent variables. In order to appropriately model the within subject covariance, the covariance structure must be pre-specified. Each model should be fit using the unstructured covariance structure. If this structure does not converge, covariance structure in the order as auto-regressive, Toeplitz structures and the compound symmetry will be used.

The LS means of MUBADA SUV_r change at each visit from the model will be displayed along with the corresponding 95% confidence intervals. In addition, p-values will be

provided for testing that whether or not the LS means at each visit is significantly different than zero.

Spaghetti plots will be generated to display the relationship of Flortaucipir SUVr change across the follow up visits, by each subject. The plot will use MUBADA SUVr as y-axis, subjects' age at each visit as x-axis, and color code according to amyloid status.

Explore Factors Associated with Flortaucipir SUVr Change using Multivariate Analysis

The analysis will be completed for AB+ subjects. A multivariate step wise selection regression model will be used to explore factors associated with the change in Flortaucipir SUVr (MUBADA). The dependent variable will be Flortaucipir SUVr (MUBADA) change at 18 months. The independent variables include baseline information such as age, cognitive assessments (MMSE), APOE4 status (carrier or non-carrier), florbetapir SUVr, and flortaucipir MUBADA SUVr. The significance level of entry and stay in the model will be both set as 0.2. For each variable in the final model, the parameter estimate, SE, 95% CI and associated p-value will be reported.

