4 STUDY DESIGN

4.1 General Design

This study is an open label, multicenter Phase 2 study. This study is conducted in two phases, an exploratory (first) phase and complimentary (second) phase. The study will enroll cognitively healthy volunteers, subjects with mild cognitive impairment (MCI) and subjects with Alzheimer's disease. Approximately 230 subjects will be enrolled in the study: 80 cognitively healthy volunteers (20 subjects who will be ≥ 20 to ≤ 40 years of age, and 60 subjects who will be ≥ 50 years of age), 80 subjects with MCI, 70 subjects with AD (60 subjects with a Mini-Mental State Examination (MMSE) ≥ 20 , and 10 subjects with an MMSE > 10 and < 20). For the 60 cognitively healthy volunteers ≥ 50 years of age, these subjects will be distributed across age deciles (50-59, 60-69, 70-79 and > 80).

All subjects will provide informed consent before starting any study procedures.

Screening assessments may take place over several days and will include demographic information, cognitive testing, safety assessment, and MRI, including both volumetric and standard clinical sequences. Subjects who qualify for the study will undergo both a florbetapir F 18 PET imaging session and a Flortaucipir PET imaging session. The imaging sessions must be performed at least 48 hours apart, but not more than 60 days apart. The order of the scans is interchangeable. Some subjects, who are ≥ 50 years of age, will have the option to also participate in cerebrospinal fluid (CSF) collection by lumbar puncture (LP).

Subjects who are ≥ 50 years of age will return for have a follow-up visits at 9 (+/-2) months 18 (+/-2) following the initial Flortaucipir scan. Cognitive assessments and updates to concomitant medications and medical history will be collected at each follow-up visit. Subjects will also have follow-up Flortaucipir scans and MRI, including both volumetric and

standard clinical sequences. A sub-set of subjects may have the option to have an additional resting state functional (rsf) MRI sequence scan in addition to the volumetric and standard clinical sequences at both the screening MRI and follow-up MRIs. Subjects or their designated decision maker will be contacted by phone at 5 and 14 months following the initial Flortaucipir scan to collect updated concomitant medications and medical history.

Florbetapir F 18 PET Imaging Session:

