4.3 Method of Assignment of Subjects to Treatment Groups

Florbetapir F 18:

All subjects will receive a single IV bolus administration target dose of 370 MBq (10 mCi) of florbetapir F 18 injection.

Flortaucipir:

All subjects except for young cognitive normal (YCN) subjects will receive a single IV bolus administration target dose of 370 MBq (10 mCi) of Flortaucipir injection at each of the baseline, 9 months, and 18 months visits. YCN subjects will only receive a single IV bolus administration of Flortaucipir injection with a target dose of 370 MBQ (10 mCi) at baseline visit.

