4.5 Determination of Sample Size

A total of 230 subjects (80 cognitively healthy volunteers, 80 MCI and 70 AD) will be enrolled in the Exploratory Phase of this study. To explore the Flortaucipir SUVR values across age strata among cognitively healthy subjects, these subjects will be divided into 5 age groups as 20-40 years old, 50-59 years old, 60-69 years old, 70-79 years old and 80 years old or above. There will be 15 subjects in each of the 50 or older age groups and about 20 subjects from age group 20-40 years old. From a preliminary analysis of study T807000, the standard deviation (SD) of SUVR from combination region of interest (ROI) was 0.06 for subjects with low probability of AD. Therefore assuming a 0.06 SD, a sample of 15 subjects will give an approximately 90% probability to observe a 95% confidence interval as accurate as +/-0.04 around the point estimation.

From previous studies, the amyloid positive rate is approximately 50% among MCI patients and approximately 80% from AD subjects. Therefore 80 MCIs and 70 ADs will likely result in 40 amyloid positive MCIs and 56 amyloid positive ADs. Also from study T807000, the combination ROI SUVR difference between CN and AD was 0.39, with a pooled SD of 0.27. Assume a pooled SD of 0.30, a sample of 60 CNs and 56 amyloid positive ADs will give a 90% power to detect a 0.18 difference between the CN and AD groups.

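### The by-visit SUVr table by amyloid status counts the roughly 20 young controls at baseline only, so its visit means are on different people by design

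*SAP*

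**What the plan says.** SAP 8.6.2.1 (longitudinal, primary efficacy variable) begins with a table of flortaucipir SUVr "by amyloid beta status (AB+, AB-) at baseline, 9 month, and 18 month across all subjects". The next sentence defines a different population for the repeated-measures model: "for all subjects except for YCN subjects (who do not have follow-up flortaucipir scans at 9 months and 18 month".

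SAP 4.3 confirms the schedule behind that exclusion: "YCN subjects will only receive a single IV bolus administration of Flortaucipir injection", at the baseline visit. The same section gives every subject an amyloid scan: "All subjects will receive a single IV bolus administration target dose of 370 MBq (10 mCi) of florbetapir F 18 injection". Each YCN subject therefore has an amyloid status and falls into one row of the table.

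The efficacy population in SAP 8.3.3 does not remove YCN. The planned numbers are "about 20 subjects from age group 20-40 years old" (SAP 4.5) and "60 subjects who will be ≥ 50 years of age" among the healthy volunteers (SAP 4.1).

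**The concern.** The table supports an objective about the rate of change of tau, and its three-visit layout invites the reader to compare means down a stratum. A whole age group that is present at baseline and absent afterwards can move the stratum mean without any subject changing. Nothing in the sentence asks for within-subject change, whereas the cognition tables in SAP 8.6.2.4.1 put change from baseline in the same table.

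The SAP itself treats YCN as not comparable with the older groups: SAP 8.6.1.1 keeps them out of the cross-sectional ANOVA because of their age. At stake is a descriptive display that may disagree with the model estimate reported beside it, for a reason that has nothing to do with tau accumulation.

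**Working it through.** **Who is in the table.** The wording could be loose shorthand for subjects aged 50 or over, so it was compared with usage elsewhere in the SAP.
- SAP 8.6.1.1 asks for scatter plots across all subjects and lists YCN among the groups, so the phrase includes YCN there.
- Where the SAP means to omit YCN it says so: in 8.6.1.3.2, in 8.6.1.3.3, and in the model sentence of 8.6.2.1.
- If the phrase only means pooled over diagnosis, YCN are still included.

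A programmer following the text would put YCN in the baseline column.

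**Inputs from the documents.** The plan gives no figure for this table, but its amyloid counts in SAP 4.5 reproduce: 80 × 0.50 = 40 and 70 × 0.80 = 56 ("Therefore 80 MCIs and 70 ADs will likely result in 40 amyloid positive MCIs and 56 amyloid positive ADs"). That leaves 40 AB- MCI and 14 AB- AD, or 54. YCN number about 20 and older controls (OCN) 60.

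**Inputs assumed, because the documents do not give them.**
- All 20 YCN are AB-.
- The OCN amyloid-positive rate p is 10%, 20% or 30%.
- The gap d is mean SUVr of older AB- subjects minus mean SUVr of YCN, taken as 0.03, 0.06 or 0.10, with zero and negative values also tried. SAP 4.5 gives an SD of 0.06 in subjects with low probability of AD; that is a spread between subjects and not an age-group difference, so it serves only as a scale.

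**Formula.** Suppose nobody changes and nobody drops out. With n older AB- subjects, the baseline mean mixes n older and 20 young subjects, and the follow-up mean uses the n older subjects alone. The apparent change is w × d, where n = 54 + 60(1 − p) and w = 20/(n + 20).

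| p | n | w | d = 0.03 | d = 0.06 | d = 0.10 |
|---|---|---|---|---|---|
| 10% | 108 | 20/128 = 0.156 | 0.0047 | 0.0094 | 0.0156 |
| 20% | 102 | 20/122 = 0.164 | 0.0049 | 0.0098 | 0.0164 |
| 30% | 96 | 20/116 = 0.172 | 0.0052 | 0.0103 | 0.0172 |

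At n = 102, d = 0 gives no shift and d = −0.05 gives −0.0082, an apparent fall. A simulation with 102 older and 20 young subjects, SD 0.06 and no within-subject change gave the same averages: +0.0049, +0.0098, +0.0164, about 0, and −0.0082.

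**Scale.** With SD 0.06 and n = 102, the standard error of the AB- mean is 0.06/√102 = 0.0059, so the shift at d = 0.06 is 0.0098/0.0059, about 1.7 standard errors. With the SD of 0.30 that SAP 4.5 assumes for its power statement, the standard error is 0.0297 and the same shift is about 0.3. Neither SD was obtained for AB- subjects on the endpoint used here. Both come from the sample-size section, which works with a combination ROI, whereas the endpoint is MUBADA SUVr with a white-matter reference (SAP 6.4.1.1).

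**After the fix.** With YCN removed, their contribution is exactly zero for any d. The AB- baseline count goes from 116-128 to 96-108, the subjects who are due for follow-up scans.

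**The case against.** The strongest objection is that nothing inferential depends on this table. The longitudinal primary objective is estimated from within-subject change, with YCN excluded, AB+ and AB- modelled separately, and LS mean changes tested against zero. A reader might infer that the primary longitudinal result is biased; the documents do not support that.

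A reader might also infer that tau will falsely appear to rise in AB- subjects. The documents do not support that either, since they give neither the size nor the sign of the SUVr gap between YCN and older AB- subjects, nor the amyloid rate in YCN.

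Nor do they support treating AB- as the reference against which AB+ accumulation is judged: SAP 8.6.2.1 specifies no contrast of change between the strata.

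The drop in numbers would also be visible. SAP 9 requires n with every continuous summary, and the spaghetti plots show each subject separately. These points limit the consequence, and they stand. They do not remove the mismatch: a falling n tells the reader that subjects are missing, but not that a whole age group is absent by design.

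The general rule in SAP 7.1, summaries by four diagnostic groups and overall, does not settle it. SAP 8.6.2.1 asks for amyloid status pooled over subjects, and an overall column would still contain YCN at baseline only.

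**Conclusion.** The point holds for the descriptive table alone. By design, its baseline column includes about 20 subjects who cannot appear at 9 or 18 months, so its visit means do not describe the same people. That follows from the text without any assumption about SUVr.

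The size and direction of the effect are conditional. If all YCN are AB- and 10-30% of OCN are AB+, YCN carry 15.6-17.2% of the AB- baseline mean. A gap of 0.03 to 0.10 then produces an apparent rise of about 0.005 to 0.017, a reversed gap an apparent fall, and no gap no shift. Any YCN who are AB+ would cause the same mismatch in the AB+ row. The model estimates and p-values are unaffected. This is a minor but worthwhile wording correction.

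**What to change.** In the first sentence of SAP 8.6.2.1, restrict the table to all subjects except for YCN, which matches the model population in the next sentence. This costs one line, and no information is lost: SAP 8.6.1.1 and 8.6.1.2 already describe YCN baseline SUVr, the latter by age group.

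Optionally, add to the same table the observed change from baseline among subjects scanned at each visit, with n, as SAP 8.6.2.4.1 does for cognition. Excluding YCN removes the planned imbalance but not ordinary dropout; a paired change column deals with both. It overlaps with the model output, so it is good table design and not a needed correction.

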8. STATISTICAL ANALYSIS

8.1. General Statistical Considerations

All statistical analyses will be performed using SAS® version 8.2 or higher.

Data will be summarized using descriptive statistics (number of subjects [N], mean, standard deviation [SD], median, quartiles, minimum, and maximum) for continuous variables and using frequency count and percentage for discrete variables. The demographic and baseline characteristics data will be summarized according to clinical

group (healthy volunteers and subjects with cognitive impairment) at recruitment for all subjects in the safety population. Safety data will be summarized for all patients.

Subject listings of all data from the electronic case report forms (eCRFs) as well as any derived variables will be presented.

Additional details concerning statistical analyses will be included in the Statistical Analysis Plan (SAP).

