8.1.2. Exploratory Phase, Cross-sectional Component

8.1.2.1. Primary Objective Analysis

ANOVA analysis will be applied to detect the difference between clinical diagnosis groups. If an overall difference is detected, pair-wised comparisons will be conducted. If the pre-requisites of ANOVA test are not met, Kruskal Wallis and Wilcoxon rank sum test will be conducted instead.

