8.1.3. Exploratory Phase, Longitudinal Component

8.1.3.1. Primary Objective Analysis

The primary objective of longitudinal component is to assess the rate of change of tau deposition as measured by ¹⁸F-AV-1451 over time. The tau measurement change from baseline at each follow up visit will be estimated using Mixed Model Repeated Measures (MMRM). The MMRM model will include the following fixed effects: baseline value, clinical group, visit, clinical group by visit interaction, and baseline age. Visit will be considered as a categorical variable. An unstructured covariance matrix will be used to model the within-subject correlation. Least squared means (LSM) and standard error for

the tau value change from baseline will be calculated for each clinical group at every follow up visit.

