5.2 Changes from the Analyses Planned in the Protocol/CIP

The protocol was amended (version 07 August 2015, Amendment 2). In this amendment the study was divided into two phases, exploratory (first) phase and confirmatory (second) phase. Currently, this SAP provides the planned analyses for the exploratory (first) phase of the study.

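### The SAP's primary longitudinal model of SUVr change omits the clinical group and group-by-visit terms that the protocol specifies, and the SAP does not record the change

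*SAP*

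**What the plan says.** Protocol 8.1.3.1 fixes both the model and its output. The model: "The MMRM model will include the following fixed effects: baseline value, clinical group, visit, clinical group by visit interaction, and baseline age". The output is an LS mean and standard error, so that the "tau value change from baseline will be calculated for each clinical group at every follow up visit".

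SAP 8.6.2.1 keeps change from baseline as the outcome and visit as a categorical factor, and leaves out young healthy volunteers because they have no follow-up scan. Citing unequal variance of SUVr change by amyloid status, it then states that "the model will be run for AB+ subjects only, and for AB- subjects only separately". The terms are baseline MUBADA SUVr "and age, and visit as independent variables". LS means are reported per visit within each amyloid stratum. The descriptive statistics follow the same layout: they "will be provided by amyloid beta status (AB+, AB-) at baseline, 9 month, and 18 month across all subjects".

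SAP 5.2, the section for departures from the protocol's analyses, notes that Amendment 2 divided the study into two phases and ends: "Currently, this SAP provides the planned analyses for the exploratory (first) phase of the study". It says nothing about the longitudinal model.

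The protocol does not define clinical group in 8.1.3.1. Section 8.1 summarises baseline data by clinical "group (healthy volunteers and subjects with cognitive impairment) at recruitment", which is two groups. Section 8.1.2.1 speaks of diagnosis: "ANOVA analysis will be applied to detect the difference between clinical diagnosis groups".

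**The concern.** Two fixed effects named in the protocol, and the per-group estimates they exist to produce, are missing from the SAP's primary longitudinal analysis. The reason given supports fitting the amyloid strata separately. It gives no ground for pooling older healthy volunteers (OCN), MCI and AD within each fit.

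Two things are at stake. First, the protocol's stated primary output will not be produced, and a reader of the SAP is not told so. Second, each stratum mean averages over diagnoses in proportions that differ between the strata. If tau change differs by diagnosis, an AB+ versus AB- comparison mixes amyloid status with diagnostic composition.

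The confirmatory phase is not affected, since its cohort has no follow-up PET.

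**Working it through.** **No stated figure for this model.** Neither document gives a sample size or power for longitudinal SUVr change. The nearest figure, in SAP 4.5, is cross-sectional: 90% power for a 0.18 difference, SD 0.30, 60 versus 56 subjects. It reproduces: SE = 0.30 × √(1/60 + 1/56) = 0.0557; 0.18/0.0557 = 3.23; power = Φ(3.23 − 1.96) ≈ 0.898. It has no bearing on the point here.

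**Step 1: the two models side by side.**

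| Element | Protocol 8.1.3.1 | SAP 8.6.2.1 |
|---|---|---|
| Fit | one model | separate fits, AB+ and AB- |
| Baseline SUVr, age, visit | yes | yes |
| Clinical group | yes | no |
| Clinical group × visit | yes | no |
| LS means | per clinical group and visit | per visit within amyloid stratum |
| Number of LS means | 2 visits × 2 or 3 groups = 4 or 6 | 2 visits × 2 strata = 4, none by clinical group |

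**Step 2: is the per-group estimate recovered elsewhere in the SAP?**

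- The stepwise regression in 8.6.2.1 has SUVr change as its outcome, but only in AB+ subjects and only at 18 months. Its candidate list is open-ended and does not name diagnosis.
- Section 8.6.2.4.1 has diagnostic groups in its title, but models psychometric change by tau and amyloid status.
- The remaining analyses in 8.6.2.4 have cognitive or functional outcomes.
- Section 8.6.1.1 compares diagnoses, but cross-sectionally.
- Section 7.1 has a general rule that values are summarised by the four diagnostic groups. At most this gives raw summaries.

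No model estimates SUVr change by clinical group.

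**Step 3: diagnostic mix within the strata.** SAP 4.5 expects 80% of 70 AD = 56 and 50% of 80 MCI = 40 to be amyloid positive. That leaves 14 AD and 40 MCI amyloid negative.

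- AD share of impaired subjects: AB+ 56/96 = 58%; AB- 14/54 = 26%.
- The amyloid-positive rate in the 60 OCN is not given. Assuming 10% to 30% (6 to 18 subjects), OCN are 6/102 = 6% to 18/114 = 16% of AB+, and 54/108 = 50% to 42/96 = 44% of AB-.

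**Step 4: do the covariates remove the mix?** No. Visit is categorical, and baseline SUVr and age are constant over visits. With complete data and a common covariance matrix, the fitted residuals therefore average zero at each visit. The LS mean at the stratum's average covariates is then the raw stratum mean, weighted by the diagnoses present.

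**Step 5: illustration.** Let MCI change be *r* times AD change, with the same *r* in both strata. The mean among impaired subjects, relative to AD change in that stratum, is (56 + 40*r*)/96 in AB+ and (14 + 40*r*)/54 in AB-.

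| *r* | AB+ | AB- |
|---|---|---|
| 1 | 1.00 | 1.00 |
| 0.75 | 0.90 | 0.81 |
| 0.5 | 0.79 | 0.63 |

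The values of *r* are assumed, and OCN are left out. The table shows how mix alone can separate the strata; it does not measure an error in either SAP estimate.

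**The case against.** The strongest reply concerns consequence. The primary longitudinal objective is the rate of tau change over time and names no comparison between clinical groups. The SAP sets out its model openly and gives a reason for the split. This is a hypothesis-generating phase in which no power, multiplicity or confirmatory claim depends on the missing terms. The general summary rule could supply raw SUVr by diagnosis, and baseline MMSE in the stepwise model carries some information on severity. All of this stands as a limit on the size of the point. None of it restores the modelled per-group estimates. Protocol 8.1 lets the SAP add detail, but deleting named fixed effects is not adding detail. Section 8.1.3.2 hands its specifics to the SAP; 8.1.3.1 does not.

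The illustration is open to criticism: *r* has no source in the documents, OCN are omitted although they may be nearly half of AB-, and the ratio means little if AB- AD change is close to zero. That is fair, and the conclusion does not rest on it.

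There is also a technical objection to restoring the terms. The pilot figures for a combination ROI (CN to AD difference 0.39, SD 0.06 in low-probability subjects) suggest little overlap in baseline SUVr. An OCN LS mean at the AB+ average baseline may therefore be an extrapolation from few subjects. This calls for caution with that cell, but the protocol's own model has the same feature, so it does not explain the unrecorded removal.

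**Conclusion.** The point holds, with high confidence on the text: the two terms are gone, no SAP model of SUVr change by clinical group replaces them, and SAP 5.2 does not say so. The loss is the whole per-group output, four or six LS means depending on how clinical group is read. The objective itself is still addressed through the two amyloid strata.

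The effect on interpretation is conditional. It arises only if change differs by diagnosis, and its size cannot be fixed from the documents. That the mix differs between strata rests on the plan's expected amyloid rates for MCI and AD; the OCN shares rest on an assumed rate. This should be corrected, but it does not invalidate the planned stratum estimates.

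**What to change.** In SAP 8.6.2.1, keep the amyloid split and the pooled stratum means. Add clinical group (OCN, MCI, AD, as in the SAP's cross-sectional analysis) and clinical group × visit to both models. Report LS mean change with 95% CI per group and visit beside the pooled means. State which grouping clinical group denotes, since Protocol 8.1 describes two groups. Record any remaining departure from Protocol 8.1.3.1 in SAP 5.2 with its reason, including that means are given within amyloid strata rather than overall.

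The cost is SAP wording and two model terms, with no new data. The drawback is wide intervals in small cells. Approximate 95% half-widths in stratum SDs of change are 1.96/√n. The second column uses 0.8n, borrowing the confirmatory phase's 20% dropout because the exploratory phase states no rate.

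| Cell (n) | No dropout | 20% dropout |
|---|---|---|
| AB+ AD (56) | 0.26 | 0.29 |
| AB+ MCI, AB- MCI (40 each) | 0.31 | 0.35 |
| AB- AD (14) | 0.52 | 0.59 |
| AB+ OCN (6, assumed) | 0.80 | 0.89 |
| AB+ OCN (18, assumed) | 0.46 | 0.52 |

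These assume one SD across diagnoses within a stratum and ignore the baseline adjustment, so they are only a guide for the smallest cells.
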